2.5.1 Methods of analysis

Comparisons will be made between all participants randomised to the different treatment arms, irrespective of whether they received their allocated treatment (“intention-to-treat” analyses).

Primary and first secondary outcome: For time-to-event analyses of the primary and first secondary outcome, the tecovirimat group will be compared with the placebo group using a stratified log-rank test (days since symptom onset ≤ 7 , >7 days). Kaplan-Meier estimates for the time to event will also be plotted (with associated log-rank p-values). The log-rank ‘observed minus expected’ statistic (and its variance) will also be used to estimate the average event rate ratio (and its confidence interval) for those allocated to treatment group versus the placebo group.

Other secondary outcomes: Time to consistently negative culture for monkeypox virus on throat swab and on swab of most recent active skin or mucosa lesion at Days 7, 14, 21, and 28 will be analysed using an interval censored Weibull model. A negative culture will be considered ‘consistently negative’ if it is not followed by a positive culture on the same type of swab during subsequent assessments.

Subsidiary and safety outcomes: Clinical status on an ordinal scale will be compared between tecovirimat and placebo groups using a proportional odds model.⁽²³⁾ Howard’s method will be used if the proportional odds assumption is not satisfied.⁽²⁴⁾ Monkeypox virus DNA concentration will be compared between groups using the Wilcoxon rank-sum test. Data on hospital admissions and safety will be analysed using Fisher’s exact test. For time-to-event analyses of the subsidiary outcome of need for analgesia, the tecovirimat group will be compared with the placebo group using a stratified log-rank test (days since lesion onset ≤ 7 , >7 days).

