2.8 Data and safety monitoring

The study will collect information on:

- (i) **Serious Adverse Events (SAE):** A SAE is any adverse event that:
 - results in death
 - is life-threatening*
 - requires inpatient hospitalisation or prolongation of existing hospitalisation
 - results in persistent or significant disability/incapacity
 - consists of a congenital anomaly or birth defect.

The MHRA SmPC will be the source of Reference Safety information (RSI).

- (ii) **Non-serious Adverse Events (NSAE):** This includes any new symptoms reported by the participant. Participants will be specifically asked about AEs of special interest, including headache, sore eyes, cough, shortness of breath, nausea, vomiting, diarrhoea, muscle aches, joint pain.

rm "life-threatening" in the definition of "serious" refers to an event in which the participant was at risk of death at the time of the event; it does not refer to an event which hypothetically might have caused death if it were more severe

(iii) **Reasons for prematurely stopping allocated study treatment.**

These will be ascertained from the weekly review calls with the participant by a study clinician (up to day 28), and spontaneous reports from healthcare professionals caring for the participant. In addition, participants (and their parents or carers if under 16) will be provided with a dedicated 24-hour phone support line for any trial-related queries, and with a wallet card containing details of the trial that they should carry with them during the 28 day follow-up period. These safety outcomes will be collected up to day 28 (i.e. 14 days after the completion of study treatment). Study staff that become aware of a potential SAE will report this within 24 hours to the Chief Investigator or their designee.

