2.9 Central assessment of SAEs and onward reporting of SUSARs

All serious adverse events (SAEs) will be documented and their causal relationship to the study treatment will be assessed by the Chief Investigator or designee. Serious Adverse Events that are believed with a reasonable probability to be due to the study treatment will be considered a Suspected Serious Adverse Reaction (SSAR) (https://database.ich.org/sites/default/files/E2A_Guideline.pdf).

Clinicians at the Central Coordinating Office are responsible for expedited review of reports of SSARs received. Additional information (including relevant medical and medication history) will be sought from relevant healthcare teams. An assessment made of whether the event is “expected” or not (assessed against the relevant Reference Safety Information*). Any SSARs that are not expected would be considered a Suspected Unexpected Serious Adverse Reaction (SUSAR).

All confirmed SUSARs will be reported to the Chair of the DMC, the trial sponsor, and to MHRA and the ethics committee, in an expedited manner in accordance with regulatory requirements.

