2.11 Blinding and Emergency Unblinding

This is a placebo-controlled trial in order to avoid knowledge about the treatment allocation impacting (or being perceived to impact) the assessment of clinical outcomes and adverse events or adherence to the study procedures (e.g. completion of questionnaires or collection of samples). While the study is in progress, access to the treatment allocation for individual participants and tabular results of study outcomes by allocated treatment allocation will not be available to anyone other than the DMC and the statistical team responsible for preparing analyses for the DMC.

There are two exceptions in which unblinding of the treatment allocation (tecovirimat or placebo) for an individual participant may be warranted:

- When knowledge of the treatment allocation could materially influence the immediate medical management (e.g. after overdose); and
- When the Chief Investigator (or delegated clinician) reviews a report of a SSAR.

An unblinding service is available on a 24-hour basis via the CCO telephone service. The treatment allocation will be provided promptly to any clinician treating a patient in the trial who requests the treatment allocation assignment in emergency circumstances.

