The safety of tecovirimat was evaluated in 359 healthy adult subjects ages 18-79 years in a Phase 3 clinical trial. The most frequently reported adverse reactions (occurring in at least 5% of subjects) were headache and nausea. Abdominal pain and vomiting each occurred in 2% of subjects. A total of 6 subjects discontinued drug due to mild adverse reactions and one abnormal EEG change. Additional details on less common adverse reactions and the adverse reactions that led to drug discontinuation are found in the TPOXX prescribing information.(2)

Tecovirimat is a weak inducer of cytochrome P450 (CYP)3A and a weak inhibitor of CYP2C8 and CYP2C19. However, the effects are not expected to be clinically relevant for most substrates of those enzymes based on the magnitude of interactions and a maximum 14-day duration of tecovirimat administration, with the exception of repaglinide and midazolam as follows.

Co-administration of repaglinide and tecovirimat may cause mild to moderate hypoglycemia. In a drug interaction study, 10 of 30 healthy subjects experienced mild (6 subjects) or moderate (4 subjects) hypoglycemia following co-administration of repaglinide (2 mg) and tecovirimat. Symptoms resolved in all subjects after intake of food and/or oral glucose.

Co-administration of midazolam and tecovirimat may reduce the effectiveness of midazolam. Effectiveness of midazolam should be monitored when administering tecovirimat with midazolam.

Refer to the tecovirimat prescribing information for additional information on drug interactions.[\(2\)](#)

Formulation, Appearance, Packaging, and Labelling

Tecovirimat is available as immediate-release capsules containing tecovirimat monohydrate equivalent to 200 mg of tecovirimat for oral administration. The capsules are imprinted in white ink with “SIGA” followed by the SIGA logo followed by “®” on an orange body, and a black cap imprinted in white ink with “ST-246®.” The capsules include the following inactive ingredients: colloidal silicon dioxide, croscarmellose sodium, hydroxypropyl methyl cellulose, lactose monohydrate, magnesium stearate, microcrystalline cellulose, and sodium lauryl sulfate. The capsule shell is composed of gelatin, FD&C blue #1, FD&C red #3, FD&C yellow #6, and titanium dioxide.

Tecovirimat capsules are supplied in 75-cc high-density polyethylene bottles fitted with a heat induction seal and child-resistant screw cap closure system.

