2.6 Outcomes

2.6.1 *Primary outcome*

Time (in days) to active lesion resolution, defined as the first day on which all skin lesions are scabbed or desquamated (and mucosal lesions healed), up to 28 days after randomisation.

2.6.2 *Secondary clinical outcomes*

- (i) Time (in days) to complete lesion resolution, defined as the first day on which all lesions are completely resolved (all scabs dropped off and intact skin remains underneath, and mucosal lesions healed), up to 28 days after randomisation
- (ii) Time to negative throat swab viral culture, defined as time to consistently negative culture for monkeypox virus on throat swab at Days 7, 14, 21, and 28
- (iii) Time to negative skin or mucosa swab viral culture, defined as time to consistently negative culture for monkeypox virus on swab of most recent active skin or mucosa lesion at Days 7, 14, 21, and 28

2.6.3 *Subsidiary clinical outcomes*

- (i) Clinical status on day 7, 14, 21 and 28 according to the following ordinal scale:
 - a. All lesions completely resolved (all scabs dropped off and intact skin remains underneath, and all mucosal lesions healed)
 - b. Active lesions resolved (all skin lesions scabbed or desquamated, but not all completely resolved)
 - c. Active lesions persist but no new lesions in last 24 hours
 - d. New active lesion(s) in last 24 hours.
- (ii) Throat swab monkeypox DNA levels: monkeypox virus DNA concentration in throat swabs at Days 7, 14, 21, 28
- (iii) Number (%) of patients admitted to hospital for a complication of monkeypox (overall and by type)
- (iv) Time to sustained absence of use of analgesia for monkeypox symptoms, defined as time to consistently reporting no use of analgesia, up to 28 days after randomisation.

2.6.4 *Safety assessments*

- (i) Number (%) of patients suffering serious adverse events (overall and by type) within 28 days of randomisation
- (ii) Number (%) of patients suffering adverse events of special interest (overall and by type) within 28 days of randomisation. These are:
 - Vomiting
 - Diarrhoea
 - Fever
 - Severe tiredness
 - Swollen lymph glands
 - Headache

- Muscle or joint pain
 - Sore eyes
 - Shortness of breath
 - Secondary skin infection
 - Pain related to monkeypox symptoms
- (iii) Number (%) of patients suffering death, overall and by cause
- (iv) Reasons for prematurely stopping allocated study treatment

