Time to sustained absence of use of analgesia for monkeypox symptoms is defined as the first day from which analgesia is consistently not required until day 28. Imputation of missing data and the method of time-to-event analysis will be as for the primary outcome above.

4.1.4 *Safety outcomes*

The number and percentage of patients suffering suspected serious adverse reactions, suspected unexpected serious adverse reactions, and death (overall and by cause), will be listed by trial allocation. Adverse events of special interest (listed in 2.6.4) and reasons for study drug discontinuation, will be presented by randomised group as counts and percentages. Where possible, the absolute risk differences will be presented with confidence intervals, analysed using Fisher's exact test.

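### SAP 4.1.4 names no analysis of all serious adverse events, and the SAP's special-interest list omits nausea and cough, which the protocol lists

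*SAP*

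**What the plan says.** **Serious events.** Protocol 2.4.4 and SAP 2.6.4 give the same first safety outcome: "Number (%) of patients suffering serious adverse events (overall and by type) within 28 days of randomisation". SAP 2.6.4 adds three more: adverse events of special interest, death, and reasons for stopping study treatment early.

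The analysis text in SAP 4.1.4 says that "patients suffering suspected serious adverse reactions, suspected unexpected serious adverse reactions, and death (overall and by cause), will be listed by trial allocation". It then presents the special-interest events of 2.6.4 and the reasons for stopping as counts and percentages by arm. Where possible it adds risk differences, confidence intervals and Fisher's exact test. SAEs as such do not appear.

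Protocol 2.9 defines the category that does appear: "Serious Adverse Events that are believed with a reasonable probability to be due to the study treatment will be considered" suspected serious adverse reactions (SSARs). On who decides, it says that "their causal relationship to the study treatment will be assessed by the Chief Investigator or designee". A suspected unexpected serious adverse reaction (SUSAR) is an SSAR that is also not expected.

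Two general statements bear on the point. SAP section 4 opens by promising an arm-to-arm comparison for every outcome on all randomised participants. Protocol 2.5.1 states: "Data on hospital admissions and safety will be analysed using" Fisher's exact test. It makes no restriction to attributed events.

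**Events of special interest.** Under protocol 2.8, participants are asked specifically about events "including headache, sore eyes, cough, shortness of breath, nausea, vomiting, diarrhoea, muscle aches, joint pain". SAP 2.6.4 gives a fixed list of 11 entries, without nausea or cough. Protocol Appendix 1 says: "The most frequently reported adverse reactions (occurring in at least 5% of subjects) were headache and nausea".

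**The concern.** Randomisation makes the arms comparable for all SAEs. It does not do so for a subset chosen by someone's view of cause. A statistician who programs from SAP 4.1.4 would produce a table of SSARs, SUSARs and deaths. The number of patients with any SAE, overall and by type, would be left to inference from general wording elsewhere.

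The nausea gap is separate. A placebo-controlled trial is well suited to estimating a common, mild drug effect in patients whose disease produces symptoms of its own. The SAP limits the by-arm tabulation to its own list, and that list lacks one of the two reactions the protocol calls most frequent. Vomiting, which Appendix 1 puts at 2% of subjects, is kept. The SAP gives no reason for the difference.

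Safety is one of the aims in protocol 2.1, and the SAP governs the main paper.

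**Working it through.** No sample size, power or alpha figure is at issue, so there is no figure of the plan to reproduce. The check sets the lists side by side.

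**Step 1. Each SAP safety outcome against SAP 4.1.4.**

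| SAP 2.6.4 outcome | Named in SAP 4.1.4? |
|---|---|
| (i) SAEs, overall and by type | No; only SSARs and SUSARs |
| (ii) Events of special interest | Yes, by arm |
| (iii) Death, overall and by cause | Yes, by arm |
| (iv) Reasons for stopping treatment | Yes, by arm |

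Three of the four are named. The missing one is listed first.

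**Step 2. Is the substitute the same quantity?** No. By protocol 2.9, SUSARs are a subset of SSARs, and SSARs are a subset of SAEs selected by a causality judgement. A non-fatal SAE judged unrelated is in outcome (i) but in none of the serious-event categories of 4.1.4.

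**Step 3. Protocol 2.8 terms against the SAP 2.6.4 list.**

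- Kept, 7 of 9: headache, sore eyes, shortness of breath, vomiting, diarrhoea, muscle aches, joint pain. The SAP merges the last two into one entry.
- Dropped, 2 of 9: nausea, cough.
- Added, 5: fever, severe tiredness, swollen lymph glands, secondary skin infection, pain related to mpox.

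Count check: 7 kept terms make 6 entries, and 6 + 5 = 11, the length of the SAP list.

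**Step 4. Effect of the additions.** Protocol 1.1 describes fever, malaise and swollen nodes in most patients, and protocol 2.4.3 calls pain very common in the current outbreak. Protocol 2.8 defines non-serious events as new symptoms. The SAP states no new-onset rule. Without one, the overall special-interest count could consist largely of symptoms present at entry.

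**Step 5. Precision of the nausea estimate that would be missing.** The 95% half-width for a risk difference, with the same rate p in both arms and n per arm, is 1.96 × √(2p(1 − p)/n).

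Inputs:
- n = 500/2 = 250, or 500 × 0.9/2 = 225 after the planned 10% losses.
- p is an assumption. Appendix 1 gives only a floor of 5%, from healthy volunteers on active drug, and the documents give no rate on placebo or in mpox patients. Twice that floor, 10%, is shown as a range.

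| p | n = 250 | n = 225 |
|---|---|---|
| 5% | 1.96 × √(0.095/250) = 0.038 | 1.96 × √(0.095/225) = 0.040 |
| 10% | 1.96 × √(0.18/250) = 0.053 | 1.96 × √(0.18/225) = 0.055 |

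The estimate would therefore carry about ±4 to ±5.5 percentage points. No similar figure can be given for SAEs, because the documents state no SAE rate.

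**The case against.** The best reply is that the plan as a whole covers SAEs. They remain an outcome in SAP 2.6.4, SAP section 4 promises a comparison of every outcome, and protocol 2.5.1 supplies a test. SAP section 1 also says that the SAP is based on the protocol. This stands to the extent that the fault is an omission in 4.1.4. It does not close the gap. The general sentence specifies no SAE table and no classification by type, and the section that should do so names other events.

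On nausea, the reply is that it is still recorded as a non-serious event under protocol 2.8, and that it would appear among the reasons for stopping if it led a patient to stop. That is true, but the SAP states no by-arm analysis of non-serious events outside its list, and the general sentence in section 4 does not reach an event that the SAP does not list.

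A reader might infer four stronger things that the documents do not support.

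- *The safety outcomes would go unreported, or the SAE comparison has been withdrawn.* Deaths, the listed special-interest events and reasons for stopping are all reported by arm, and SAEs stay in the outcome list.
- *Every SAE judged unrelated is lost.* Deaths are reported whatever their attribution. Admissions for mpox complications, which are SAEs by protocol 2.8, are a separate outcome (SAP 2.6.3), and protocol 2.5.1 gives a test for them.
- *Unblinding shapes which events become SSARs.* Protocol 2.11 allows unblinding "When the Chief Investigator (or delegated clinician) reviews a report of a SSAR". In protocol 2.9 the causality judgement comes before that review, so on the stated sequence attribution is made first.
- *The added mpox symptoms dilute the other comparisons.* Events are reported by type as well, so only the overall count is affected. The protocol's list is open-ended, so the additions do not contradict it.

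**Conclusion.** The point holds as two gaps between outcome definition and analysis.

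- SAP 4.1.4 names no analysis for one of four safety outcomes, the first listed. For serious events it specifies only causality-judged subsets and death.
- The SAP's closed list omits two of the protocol's nine special-interest terms. One is nausea, so no by-arm nausea comparison would be produced.

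The first gap is partly covered by general wording in SAP section 4 and protocol 2.5.1. The second is not. The primary efficacy result is unaffected, but the safety tables in the main paper are affected, so this should be corrected.

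The nausea precision rests on an assumed rate of 5% to 10% in both arms and on 225 to 250 patients per arm. The size of the SAE gap cannot be computed from the documents. The case report forms were not available, so whether nausea and cough were captured is unconfirmed, although protocol 2.8 requires participants to be asked about them.

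**What to change.** 1. In SAP 4.1.4, state that patients with any SAE, overall and by type, within 28 days of randomisation will be compared between arms on all randomised participants, regardless of attribution. Keep SSARs and SUSARs as additional listings.
2. In SAP 2.6.4(ii), restore nausea and cough to match protocol 2.8, after confirming that the electronic forms capture them. If they do not, say so and give the reason for the difference.
3. Count special-interest events as new-onset, in line with protocol 2.8, so that symptoms present at entry do not dominate the overall count. Protocol 3.3 records signs and symptoms of mpox at baseline. Check that this covers each listed event.

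The cost is SAP wording and a few more rows in the safety tables. If the forms capture what protocol 2.8 requires, no new data collection is needed.

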4.2 Pre-specified subgroup analyses

Pre-specified subgroup analysis will be conducted for the primary outcome using the statistical test for interaction (or test for trend where appropriate). Results will be presented on forest plots as event rate ratios with confidence intervals. The following subgroups will be examined based on information at randomisation:

- Age (<18, 18-39, ≥40)
- Sex (male/female)
- Orthopoxvirus vaccination status (ever received yes/no)
- Time since onset of first lesion (≤7 days or >7 days)

4.3 Adjustment for multiple testing

A step-down approach will be used to control the family-wise error rate across the primary and three secondary outcomes: Hypothesis testing will first be conducted for the primary (time to active lesion resolution). Only if the null hypothesis is rejected at a 2-tailed $p=0.0476$, confirmatory analysis of the three secondary endpoints will be performed at a 2-tailed $p=0.0476$. To account for multiplicity of testing of the three secondary endpoints, the Benjamini-Hochberg method will be used.⁸ For all other assessments (including those of subsidiary, safety, and exploratory assessments and any subgroup assessments) due allowance will be made in their interpretation for multiple comparisons.

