2.8 Sample size

For the log-rank test of the primary endpoint ‘time to active lesion resolution’, the two key determinants of power are the total number of active lesion resolution events and the treatment-to-control ratio of the rate of active lesion resolution.

Table 1 displays the power of this test for various scenarios. In total, 318 patients with lesion resolution by day 28 are needed to detect a 40% improvement in the rate of lesion resolution as measured by the rate ratio (akin to a “hazard ratio” but for a positive outcome instead of death; values greater than one indicate improved outcomes) with at least 85% power and a two-sided α of 0.05. Conservatively assuming that the observed event rate of 77% from the 2007-2011 INRB/USAMRIID observational study will apply to the combined time to event data of experimental and control groups yields a total targeted sample size of 413 participants.³ A total sample size of 500 is planned to account for one interim analysis and approximately 10% losses to follow-up.

Table 1. Number of events needed to have 80% and 85% power at $2P=0.05$ to detect an improvement in the primary outcomes.

Rate Ratio	Scenario for 80% Power ($\beta=0.20$)		Scenario for 85% Power ($\beta=0.15$)	
	Number of Events Needed	Number of Patients Needed*	Number of Events Needed	Number of Patients Needed*
1.30	457	594	522	678
1.40	278	362	318	413
1.50	191	249	219	285

* Assumes that 77% of patients will experience the event and does not account for potential dropout. In the 2007-2011 INRB/USAMRIID observational study, 77% of patients reached lesion resolution (as defined above) within 22 days.

Since the event rate is uncertain, the sample size will be reviewed and revised based on blinded data (i.e. with time to event data for the experimental and control groups combined), when about 50% of the originally planned number of participants have reached determination of the primary endpoint.

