2.12 Data monitoring

During the study, interim analyses of unblinded study data (including information on the pre-specified primary, secondary and safety outcomes) will be supplied in strict confidence to the independent DMC. The DMC will request such analyses at a frequency relevant to the stage of the study and the speed and volume of new information (typically every 6 months with a Chair's review at 3 months) or in response to emerging information from other studies.

The DMC will independently evaluate these analyses and any other information considered relevant. The DMC will review the analyses among children (age <18 years) both separately and combined with the adult data. The DMC is expected to advise the Chief Investigator and Chair of the Trial Steering Committee if, in the view of the DMC, there is compelling evidence of *hazard* that seems likely to outweigh any potential benefit (either overall or in a particular subgroup of participants).

A single interim assessment for *benefit* is to take place when 50% of the originally planned number of participants have reached determination of the primary endpoint (i.e. experienced active lesion resolution before or at day 28 or reached 28 days of follow-up). A group sequential design was used to generate asymmetric two-sided boundaries based on Hwang-Shih-DeCani alpha and beta spending functions for efficacy and non-binding futility assessments (Table 2).⁴

Table 2. DMC guidance for interim analysis of benefit

		Lower bounds (futility assessment)		Upper bounds (efficacy assessment)	
Analysis	N	Z-statistic	P-value*	Z-statistic	P-value*
Interim	216	0.42	0.6616	2.75	0.0030
Final	432	1.98	0.9762	1.98	0.0238

*One-sided p-values; the one-sided p-value of the final analysis of 0.0238 corresponds to a two-sided p-value of 0.0476. Boundaries estimated using R package gsDesign

The DMC will assess the effect of tecovirimat vs. placebo on the primary outcome against these criteria and advise the Chief Investigator accordingly. In considering its recommendations, the DMC should also take account of the totality of the evidence from the trial data (including effects on secondary and other outcomes and in key participant subgroups) and any other information from external sources that it considers relevant (e.g. results from other trials, emerging information on the nature of the disease and its epidemiology).

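### No level is stated for the secondary outcomes if the trial stops early for benefit; the only level given, 0.0476, belongs to the final look, and using it at the interim modestly inflates false benefit claims

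*SAP*

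**What the plan says.** SAP 4.3, repeated in protocol 2.5.1, makes a family-wise claim: "A step-down approach will be used to control the family-wise error rate across the primary and three secondary outcomes". The gate is the primary outcome ("Only if the null hypothesis is rejected at a 2-tailed" p of 0.0476), after which "confirmatory analysis of the three secondary endpoints will be performed at a 2-tailed" p of 0.0476. Within the family, "To account for multiplicity of testing of the three secondary endpoints, the Benjamini-Hochberg method will be used". No other level appears in that section, and the interim look is not mentioned there.

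SAP 2.12 and protocol 2.10 plan one interim look for benefit, at half the planned participants. Table 2 sets the efficacy bounds at Z 2.75 (one-sided 0.0030) at the interim and Z 1.98 at the end, with the footnote that "the one-sided p-value of the final analysis of 0.0238 corresponds to a two-sided p-value of 0.0476". The DMC is asked to hold the primary outcome against these bounds. No bound or spending function is given for a secondary outcome, and nothing says that secondary tests become descriptive after an early stop.

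**The concern.** A primary result that crosses Z 2.75 at the interim also satisfies the 0.0476 gate. Followed literally, the rule then tests the secondary outcomes at 0.0476 on interim data, a level that was derived for the other look.

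Gating on the primary does not remove the problem. If tecovirimat truly speeds active lesion resolution, the gate can open at either look. It opens early when the interim primary statistic is high, and a positively correlated secondary statistic tends to be high at the same moment. The look at which the secondary is judged is therefore selected in its favour.

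At stake is a confirmatory benefit claim on a secondary outcome, made after an early stop, with a higher chance of being false than the plan implies. If the level is left open, it would have to be chosen once the interim result is known.

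**Working it through.** **Inputs.** From SAP 2.8: "318 patients with lesion resolution by day 28 are needed to detect a 40% improvement in the rate of lesion resolution", "with at least 85% power and a two-sided α of 0.05", and a 77% event rate. From Table 2: interim 216 and final 432 participants (information fraction 0.5), bounds 2.75 and 1.98, non-binding futility (ignored below). Assumed: the correlation ρ between primary and secondary statistics, which the documents do not give.

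**Reproducing the plan's figures.**
- Events: 4(1.960 + 1.036)² / (ln 1.40)² = 317.2, rounded up to 318; 318 / 0.77 = 413. Both match.
- Interim alpha, Hwang-Shih-DeCani with γ = −4 (γ is not stated; this value reproduces Table 2): 0.025 × (1 − e²) / (1 − e⁴) = 0.00298, so Z = 2.750. The final bound is then Z 1.981, one-sided 0.0238, two-sided 0.0476. All match.
- Total one-sided error for the primary with 2.75 and 1.98 is 0.0251, so Table 2 spends 0.025 in the benefit direction.

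**Primary effect at the design alternative.** The expected final Z that gives 85% power with these bounds is 3.06. As a check, 432 × 0.77 = 332.6 events, and ln(1.40) × √332.6 / 2 = 3.07. The chance of an efficacy stop at the interim is about 0.28.

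**Error for one truly null secondary under the literal rule.** Let Z₁, Z₂ be the primary statistics and S₁, S₂ the secondary statistics at the two looks, with correlation ρ at the same look and √0.5 between looks for the same outcome:

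error = P(Z₁ > 2.75, S₁ > 1.98) + P(Z₁ < 2.75, Z₂ > 1.98, S₂ > 1.98)

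At rate ratio 1.40 and ρ = 0.7, for example, the two terms are about 0.022 and 0.006, together 0.028. In the table, the last two columns are also maximised over the primary effect.

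| ρ | Literal rule, RR 1.40 | Literal rule, maximum | Interim Z 2.75 for the secondary | Pocock-type Z 2.178 at both looks |
|---|---|---|---|---|
| 0.3 | 0.0251 | 0.0256 | 0.0155 | 0.0159 |
| 0.5 | 0.0272 | 0.0272 | 0.0165 | 0.0169 |
| 0.7 | 0.0281 | 0.0294 | 0.0181 | 0.0184 |
| 0.9 | 0.0269 | 0.0332 | 0.0211 | 0.0208 |

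As ρ approaches 1 the last two columns reach 0.0247 and 0.0245. The literal rule passes 0.025 at ρ of about 0.21. With no interim look the error is about 0.024, so the excess comes from using the final level at the early look.

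**Two-sided error.** For one null secondary, adding the harm direction gives at most about 0.048 (at ρ = 0 with a large primary effect, where it is simply twice the 0.0239 tail beyond 1.98). It is lower at higher ρ, because the gate opens only for benefit.

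**Effect of Benjamini-Hochberg.** Its steps are 0.0476/3 = 0.0159, 0.0317 and 0.0476, so one outcome gets the full 0.0476 only when the other two are also rejected. The table therefore describes one null secondary alongside two effective ones; simulating that case with Benjamini-Hochberg gave maxima of 0.0271, 0.0294 and 0.0333 at ρ = 0.5, 0.7 and 0.9. With all three null, the one-sided family error reached 0.0274 in the cases tried, against 0.0238 or less with no interim.

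**The case against.** **The plan is silent rather than wrong.** SAP 4.3 uses 0.0476 for the primary gate too, although the interim primary bound is 2.75, so the section reads naturally as final-analysis text that omits the interim. This stands: the documents do not say in words that 0.0476 applies after an early stop. It is nevertheless the only level they give.

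**The stated alpha is two-sided, and on that scale one null secondary shows no breach.** This also stands. The case rests on the benefit direction, which is the direction in which Table 2 spends one-sided 0.025 and in which a secondary claim would be made.

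**The excess is small.** At the design effect it is at most about 0.003 above 0.025, and it vanishes at low correlation. High correlation is plausible for complete lesion resolution, which uses the same daily reports, imputation and test as the primary. The documents offer no basis for assuming it for viral culture. Participants still in follow-up at the interim would, if added to the analysis, weaken the selection; the documents do not describe how such data are handled.

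A reader might also infer that each secondary gets two tests. It does not: a trial that stops has no second test, and one that continues has not opened the gate.

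**Conclusion.** The gap is real and its consequence modest. The plan claims family-wise control but gives no level derived for the secondary outcomes in an outcome it plans for, an early stop for benefit (chance about 0.28 at a rate ratio of 1.40). Taken literally, the rule gives a one-sided error for a null secondary of about 0.025 to 0.028 at that effect, for correlations of 0.3 to 0.9. Maximised over the primary effect, it is 0.027 to 0.033 for correlations of 0.5 to 0.9. These figures assume bivariate normal statistics, information fraction 0.5 for both outcomes, and a correlation the documents do not supply.

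Stronger readings are not supported:
- The error does not double. The ceiling of about 0.040 requires correlation 1 together with a real primary effect and an exactly null secondary.
- Because "the sample size will be reviewed and revised based on blinded data", one might infer that the fixed final level of 0.0476 is itself a serious flaw. If the information fraction fell to 0.43, the two-sided alpha for the primary would be 0.0506, against 2 × 0.0251 = 0.0502 at 0.5, which is negligible.
- This point is not the whole of the family-wise question. Benjamini-Hochberg controls the false discovery rate; with one effective and two independent null secondaries, the one-sided family error is about 0.0315 with no interim at all. That is a separate point.

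**What to change.** In SAP 4.3 and protocol 2.5.1, state that 0.0476 applies only at the final analysis. Add that after an efficacy stop at the interim the primary is judged at Z 2.75 and the secondary family is tested at a pre-stated group-sequential level. This could be the same interim level (two-sided 0.0060, with 0.0476 kept for the final look) or a separate spending function, such as a Pocock-type level of two-sided 0.0294 at both looks. Either keeps the one-sided error for a single null secondary at or below 0.025. It would help to say in the same place how data arriving after the interim cut-off enter the secondary analyses.

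The cost is a few sentences, to be written before any unblinded interim result is known. The 0.0060 option lowers secondary power only if the trial stops early. The Pocock-type option is more lenient at the interim but also lowers the final level from 0.0476 to 0.0294. Neither makes the family-wise claim true by itself; that also needs a family-wise method such as Holm or Hochberg in place of Benjamini-Hochberg.
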